## **2. OBJECTIVES AND ENDPOINTS**

### **2.1 PRIMARY OBJECTIVE(S)**

This study seeks to demonstrate that the laboratory can mitigate respiratory virus transmission in underserved populations by using laboratory data to identify communities at risk for increase vial activity (hot spots) and intervening with a test-to-treat model provides increased access to influenza diagnostics and treatment in vulnerable and underserved communities.

1. The hot-spot frequency and hot spot score trend will be measured for each census tract to determine if the screen and treat intervention has an impact on reducing hot spot identification or hot spot score.
  - a. Following each mobile intervention, we will evaluate the hot spot score for the census tracts receiving a mobile screen and treat intervention and SVI-matched census tract not receiving an intervention for 14-days following the screen and treat intervention.
  - b. Patients will receive a follow-up phone call 14-days following their initial screening visit to assess patient and household symptoms and the socioeconomic impact of their test result and treatment access.

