Study ML44485 was therefore designed to use our Respiratory Infection Hot Spot Algorithm that identifies and supports deployment of mobile testing units to community centers, parks and senior centers in socially and economically disadvantaged communities to deploy a mobile test-to-treat model for Influenza A&B, along with testing for SARS-CoV-2 in socially vulnerable communities. This study will target communities with high rates of respiratory infection or insufficient testing for a screen and treat program for influenza. Matched communities based on the census track-based SVI will be compared to assess impact of the screen and treat program on influenza rates at a population level.

This study seeks to demonstrate that the laboratory can mitigate respiratory virus transmission in underserved populations through (1) use of analytics to identify

communities that are at risk for uncontrolled viral spread and (2) patient perception of a mobile screen and treat model for influenza.

In summary, there is a strong rationale and a positive benefit risk assessment for studying Xofluza in a screen and treat model for socially vulnerable communities and results from the Hayden et al study suggests that Xofluza has an acceptable clinical safety profile and could benefit patients who test positive for influenza. The benefit-risk ratio for Xofluza is expected to be acceptable in this setting.

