## **3. STUDY DESIGN**

### **3.1 DESCRIPTION OF THE STUDY**

We have developed an analytic algorithm that uses measures from the CDC COVID-19 Hot Spot Criteria and Brown University School of Public Health to determine COVID-19 and Influenza Hot Spots and Testing Deserts, respectively.

The Hot Spot designation was based on the CDC county-specific Hot Spot criteria that has been used to deploy resources for interventions (i.e., laboratory testing, community mitigation, health communications and health care) specific needs for the communities of interest. The CDC hot spot criteria is based on COVID-19 rates at the county level. We have adapted these criteria in several ways: (1) we have narrowed the scope of the population of interest to the census tract (2) we have included influenza transmission data (3) we have based our calculations on the proportion of the respiratory virus testing performed by TriCore Laboratories relative to the total testing in the State of New Mexico (approximately 40%) and (4) we have incorporated social determinants of health data to aid in identifying the most vulnerable community. The adaptations to the criteria allows interventions to focus on a concentrated community and deliver the interventions in places that the community is already engaging, such as community centers, senior centers and parks. The identification of communities with insufficient testing to assess the respiratory virus transmission rate, or testing deserts, in our algorithm is based on the Brown University School of Public Health testing targets which has identified a goal of 532/100,000 or 1582/100,000 COVID-19 or influenza tests for as the minimum target or suppression target, respectively. The algorithm also incorporates the social vulnerability index in the testing desert tool.

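### The primary objective can be answered by either of two tract measures with no rule for which decides, Section 6 names no primary variable, and the outcome score is not tied to one virus or to a baseline

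*Combined protocol and SAP*

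**What the plan says.** **Measures.** Section 2.1 item 1 states that "The hot-spot frequency and hot spot score trend will be measured for each census tract", in order to "determine if the screen and treat intervention has an impact on reducing hot spot identification or hot spot score". Item 1a takes only the score into a comparison, between each intervention tract and an "SVI-matched census tract not receiving an intervention for 14-days following the screen and treat intervention". It names no time point, summary statistic or baseline. Item 1b places the 14-day phone call, on symptoms and socioeconomic impact, under the same primary objective.

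**Section 6.** Section 6.2 says that individual efficacy will not be assessed and names no variable. Section 6.3, under a heading for secondary variables, gives the plan's only list of efficacy variables: census tracts and the hot spot and testing-desert scores. Hot-spot frequency is absent. Section 6.5 mentions the hot spot score alone and gives no model, test or significance level.

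**Virus.** Section 3.1 says that the algorithm serves to "determine COVID-19 and Influenza Hot Spots and Testing Deserts, respectively", and describes its adaptation of COVID-19 criteria with the words "we have included influenza transmission data". Section 2.1 aims to "demonstrate that the laboratory can mitigate respiratory virus transmission in underserved populations by using laboratory data". Section 1.3 repeats that broad aim but also says: "Matched communities based on the census track-based SVI will be compared to assess impact of the screen and treat program on influenza rates".

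**Selection and matching.** Sections 3.1 and 6.1 choose communities because they meet hot-spot or testing-desert criteria, with SVI as an added weight in the score. Comparators are matched on SVI only (Sections 1.3 and 2.1).

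**The concern.** Two analysts could both follow this plan and report different primary results. One could report a fall in how often tracts are flagged, another a fall in the score. Either could take the score as a 14-day mean, a last value, a slope or a change from before deployment.

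The virus matters because Xofluza is given only to influenza-positive subjects, and those positive for SARS-CoV-2 are referred elsewhere. If the score pools the two, it can move for reasons unrelated to the study treatment.

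The testing-desert score is a different kind of problem: the mobile unit adds tests, and so can change that score without any change in transmission.

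The choice of contrast matters because the two groups of tracts are not chosen alike. Tracts picked at a high point tend to start higher than their SVI matches and to fall back afterwards. Depending on how baseline is handled, the same data could make the programme look harmful or helpful.

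**Working it through.** The plan states no alpha, power, effect size, SD or score scale for the tract outcome, so there is no figure of its own to reproduce. Steps 2 to 4 are illustrations on stated assumptions.

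**1. Which measure is primary?**

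| Place | Frequency | Hot spot score | Desert score | Called primary? |
|---|---|---|---|---|
| 2.1 item 1 | yes | yes (trend) | no | both, joined by *or* |
| 2.1 item 1a | no | yes (14 days) | no | no rule given |
| 6.2 | no | no | no | no |
| 6.3 | no | yes | yes | no, secondary heading |
| 6.5 | no | yes | no | no |

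The hot spot score recurs most often, but no line makes it decisive or says what becomes of the others.

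**2. Size of the contrast problem.** Assume a standard normal score, the top 20% of tracts selected on it, comparators drawn from the rest, no treatment effect, and pre/post correlation r.

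- Mean of the selected tracts: 1.40 SD. Mean of the rest: -0.35 SD. Baseline gap: 1.40 - (-0.35) = 1.75 SD.
- Bias of a post-only comparison: 1.75 × r. Bias of a simple change: 1.75 × (r - 1).

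| r | Post-only (against the intervention) | Change (in its favour) |
|---|---|---|
| 0.3 | 0.52 | 1.22 |
| 0.5 | 0.87 | 0.87 |
| 0.8 | 1.40 | 0.35 |

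A simulation with 140 tracts, 28 of them selected, agrees to within about 0.01 SD. If half the selected tracts are deserts unrelated to the score, the gap falls to 0.96 SD, the post-only bias to 0.29-0.77 SD and the change bias to 0.67-0.20 SD. The directions stay the same.

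**3. Is baseline adjustment enough?** Without an SVI component in the score, adjusting for the pre-deployment score removes the bias. Section 3.1, however, makes SVI a weighted part of the score, with the weight not given. Assume that SVI explains 25%, 50% or 75% of score variance and that each selected tract is matched to its nearest neighbour on SVI. The baseline gap is then 1.49, 1.27 or 1.08 SD. Adjusting for the pre-deployment score alone leaves up to about 0.2 SD in the intervention's favour. A pair-difference version leaves up to about 0.27 SD against it. Adding SVI as a covariate brings the bias to within about 0.02 SD.

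**4. Either/or rule.** Assume a two-sided 5% test on each of the two measures, with a fall on either counting as success.

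- False claim of a reduction: 1 - 0.975² = 4.9% if independent, falling to 2.5% if perfectly correlated.
- False positive in either direction: 1 - 0.95² = 9.75% if independent, falling to 5%.

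**5. Can deployment change the desert score?** Section 6.1 gives 50-100 patients a week over at least two deployments, so 25-50 each, or 50-100 per deployment in its table. It puts a tract at 2,500-4,000 people. The smallest case is 25/4,000 = 625 tests per 100,000 and the largest is 100/2,500 = 4,000, if all attendees live in the tract and are counted. The Section 3.1 minimum target is 532 per 100,000, with no stated period. Over a 14-day window these tests supply 117%-752% of it if it applies once, 59%-376% if weekly (target 1,064) and 8%-54% if daily (target 7,448). The share is uncertain. The direction is not.

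**The case against.** The text is less open than a quick reading suggests. Item 1a is a sub-item of item 1, so the 14-day score can fairly be read as how the trend is assessed, not as a rival measure. Item 1a and Section 6.5 take only the hot spot score into the matched comparison, and Section 1.3 gives influenza rates as that comparison's target. A sensible analyst would probably choose the influenza hot spot score. This stands as a lean. But no passage calls the score primary, and Section 1.3 never links influenza rates to it.

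The objective also covers better access to diagnostics and treatment. For that aim, extra tests in a testing desert are the intended effect. This stands too: the desert score fails as evidence on transmission, not as a description of access.

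Finally, the bias figures depend on assumptions that the plan neither confirms nor excludes: selection on the score itself, linearity and the share selected. That is right, and they should be read for direction and rough size only.

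**Conclusion.** The plan does not fix what decides its primary question, which virus the deciding score covers, or how baseline enters. This should be corrected before analysis. Under the assumptions in steps 2 and 3, the unstated choice between a post-deployment comparison and a change from baseline moves the result from about 0.5-1.4 SD against the intervention to about 1.2-0.35 SD in its favour, with no true effect.

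A reader might infer more than the documents support:

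- **That a stated error rate is breached.** The plan sets no test and no alpha. Even on the assumed 5% tests, the 9.75% figure counts both directions. False claims of a reduction are about 2.5%-4.9%.
- **That the score does pool SARS-CoV-2.** The documents leave this open. They do not say that it does.
- **That adjusting for the pre-deployment score alone removes the bias.** It need not, because SVI is part of the score.
- **That the testing-desert score has no place in the study.** The access aim gives it a descriptive use.

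**What to change.** Amend Sections 2.1, 6.2, 6.3 and 6.5 as follows.

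1. Name one primary endpoint: the mean influenza hot spot score of the tract over the 14 days after deployment. Compare it with the SVI-matched tract in a model that adjusts for both the pre-deployment score and SVI.
2. Make hot-spot identification or frequency, any SARS-CoV-2 or pooled score, and the 14-day call outcomes of item 1b secondary. Report each virus separately.
3. Do not use the testing-desert score as evidence of reduced transmission. Keep it for site selection and as a descriptive measure of access.
4. State in advance whether positives found by the mobile unit count in the primary score. Report the other version as a sensitivity analysis only.

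The cost is wording in four sections and a database query. About 140 tracts are already to be tracked (Section 4.1) and the database is longitudinal and geocoded (Section 3.1), so a pre-deployment score should be obtainable. It must be confirmed that the database separates the viruses and flags mobile-unit tests. The sponsor gives up one route to a positive claim.

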### **2.2 SECONDARY OBJECTIVE(S)**

1. Secondarily, this study seeks to understand patient perception of a mobile screen and treat model for influenza, and patients will be provided a survey to better understand their experiences in access to testing for COVID and influenza and access to therapeutics for influenza at a mobile screen and treat unit.
2. All patients will be provided a survey to better understand their experiences in access to testing and therapeutics for COVID and influenza at a mobile screen and treat unit.

## **3. STUDY DESIGN**

### **3.1 DESCRIPTION OF THE STUDY**

We have developed an analytic algorithm that uses measures from the CDC COVID-19 Hot Spot Criteria and Brown University School of Public Health to determine COVID-19 and Influenza Hot Spots and Testing Deserts, respectively.

The Hot Spot designation was based on the CDC county-specific Hot Spot criteria that has been used to deploy resources for interventions (i.e., laboratory testing, community mitigation, health communications and health care) specific needs for the communities of interest. The CDC hot spot criteria is based on COVID-19 rates at the county level. We have adapted these criteria in several ways: (1) we have narrowed the scope of the population of interest to the census tract (2) we have included influenza transmission data (3) we have based our calculations on the proportion of the respiratory virus testing performed by TriCore Laboratories relative to the total testing in the State of New Mexico (approximately 40%) and (4) we have incorporated social determinants of health data to aid in identifying the most vulnerable community. The adaptations to the criteria allows interventions to focus on a concentrated community and deliver the interventions in places that the community is already engaging, such as community centers, senior centers and parks. The identification of communities with insufficient testing to assess the respiratory virus transmission rate, or testing deserts, in our algorithm is based on the Brown University School of Public Health testing targets which has identified a goal of 532/100,000 or 1582/100,000 COVID-19 or influenza tests for as the minimum target or suppression target, respectively. The algorithm also incorporates the social vulnerability index in the testing desert tool.

Using a longitudinal patient database with an active system to prospectively geocode addresses entered into our system, we are able to determine, at the census tract level, neighborhoods that are at high risk for viral transmission because they are a hot spot or testing desert. We are then able to incorporate the social vulnerability index as an additional weighted measure to the hot spot or desert score in order to calculate an identified hot spot or desert risk for a census tract. Through collaboration with local community centers, we are able to deploy a mobile testing unit to a community center, park or senior center that is in close proximity to the identified neighborhood for rapid onsite testing for Influenza A&B and SARS-CoV2 using the cobas Liat system.

New Mexico has adopted “New Mexico Board of Pharmacy Protocol for Pharmacists Prescribing of Dangerous Drugs in Conjunction with Point of Care Testing” (NMBOP POCT Protocol, Appendix 5) that allows pharmacists the prescriptive authority to prescribe Influenza antiviral therapy in conjunction with a positive point of care test (POCT). TriCore employs two (2) on-site clinical pharmacists who will follow all of the pharmacist mandates included in the regulation to prescribe and distribute Xofluza according to the approved protocol in the test-to-treat model presented in this study. The NMBOP PCOT Protocol documents the eligibility and requirements of the certified prescribing pharmacists (pharmacist) following this protocol.

The pharmacist will perform a screening physical assessment, health assessment and medical history for the patient. If the subject meets the inclusion criteria, they will have a point of care test performed. If the subject meets the exclusion criteria, they will be excluded from the study. Testing will be performed using the cobas® SARS-CoV-2 & Influenza A/B assay on the cobas® Liat® system from a self-collected nasal swab. Subjects who test positive for influenza A or B will be prescribed Xofluza with no additional refills. The pharmacist will follow-up with the patient 24-48 hours following administration for evaluation of

signs/symptoms and will refer the patient to their primary care provider, provider, or clinic for recommended laboratory testing and follow-up if appropriate.

All subjects eligible for Xofluza will receive patient education and counseling on drug information, adherence, side effects, and other patient educational materials, as appropriate. All subjects eligible for influenza antiviral therapy, but having contraindications to the therapy, or do not wish to use the therapy will be referred to their primary care provider, provider, or clinic for further evaluation.

Subjects testing positive for SARS-CoV-2 will be preferred by the pharmacist to the subjects' primary care provider, provider, or clinic for further medical assessment and follow-up, if appropriate. Subjects testing negative for all targets (SARS-CoV-2 and Influenza A&B) with a high index of suspicion for influenza, will be referred by the pharmacist to the subjects' primary care provider, provider, or clinic for further medical assessment and follow-up, if appropriate. All subjects will receive a follow-up call 14-days following the study visit to assess their symptom resolution and the impact of their illness on their well-being (Appendix 1).

The mobile testing unit will be deployed a minimum of 2 times per week following the determination of the influenza season by the New Mexico Department of Health. We expect to screen 50-100 patients per week for the duration of the influenza season (approximately 12 weeks) for a total of 600-1,2000 patients. With an anticipated 10% positivity rate for influenza, we expect at least 5-10 patients per week to be eligible for treatment for a total of 60-120 subjects eligible over the course of the study. All subjects will be provided a survey to evaluated their ability to access respiratory virus testing and their acceptance of and trust in using a mobile unit for access to treatment and therapeutics. Patients positive for SARS-CoV-2 will be counseled on options for treatment and follow up for COVID-19 infection. All subjects enrolled in the study will receive a follow-up phone call 14-days following the initial screening visit.

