## **6. STATISTICAL CONSIDERATIONS**

### **6.1 DETERMINATION OF SAMPLE SIZE**

The algorithms that we use to determine the community of interest is based on meeting the hot-spot or testing desert criteria and a weighted value of the social vulnerability index (SVI) which defined from 0-1.0 and is determined at the census tract level. This includes factors such as socioeconomic status, household composition, race/ethnicity, housing and transportation access. Each census tract is composed of 2500-4000 individuals and we anticipate enrolling 200-250 patients at each deployment resulting in approximately 5-10% of the census tract tested at each deployment. The 20 community centers that we will partner with have an average SVI pf 0.85 (0.55-1.0). There are

approximately 140 census tracts in the Albuquerque Metropolitan Area that will be tracked during this study. These high vulnerability locations are aggregated in six zip codes with the following demographic composition of race and ethnicity.

While test positivity rate will change based on the current epidemiology, we expect 10-20% positivity for Influenza during the treatment study period as we anticipate beginning the study period during respiratory virus season with increased viral positivity. Based on this, we expect 20-50 patients will be eligible for influenza treatment at each deployment with an additional 20-50 patients positive for COVID-19 who will receive referrals for COVID-19 treatment at other treatment locations. We expect that we will be able to provide treatment to approximately 430 individuals based on the assumption that 90% will be in the treatment window and 80% will test positive.

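### The tract-level hot-spot comparison has no pooling across tracts and no measure of chance variation, although a tract may yield only a few laboratory influenza positives per 14-day window.

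*Combined protocol and SAP*

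**What the plan says.** Section 3.1 adapts the county hot-spot criteria in four ways. The first is "we have narrowed the scope of the population of interest to the census tract"; another bases the calculations on the laboratory's share of state testing, about 40%. The same section gives two testing targets, "goal of 532/100,000 or 1582/100,000 COVID-19 or influenza tests for as the minimum target or suppression target, respectively", with no time unit for either. Section 6.1 adds that "Each census tract is composed of 2500-4000 individuals" and that "we expect 10-20% positivity for Influenza during the treatment study period".

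Under 2.1, "The hot-spot frequency and hot spot score trend will be measured for each census tract", and this is meant to show whether the intervention reduces hot-spot identification or score. Item 1a sets the comparison: visited tracts beside an "SVI-matched census tract not receiving an intervention for 14-days following the screen and treat intervention". Section 6.3 names census tracts and their scores as the efficacy variables. Section 6.5 is one sentence about measuring the score in the paired tracts. About 140 tracts are tracked (4.1, 6.1).

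The document contains no score formula, minimum count, pooling rule, model, interval or test for this comparison.

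**The concern.** A criterion that is stable for a county can be unstable for a few thousand people seen through one laboratory. If a tract's score rests on a handful of positives, its flag can clear, or its score fall, with no change in transmission. The same noise can hide a real fall. The primary objective is meant to demonstrate an effect on hot spots, yet nothing in 2.1 or 6.5 separates such movements from an effect. The question is how few positives a tract is likely to have, and how often chance alone would look like improvement.

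**Working it through.** **A figure the plan states.** The only stated figure built on tract population is the share tested per deployment, about 5-10% (6.1). It reproduces: 200/4,000 = 5% and 250/2,500 = 10%. The plan gives no expected count of positives per tract.

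**Inputs.** Tract population 2,500-4,000 (6.1); targets 532 and 1,582 per 100,000 (3.1); laboratory share 0.40 (3.1); influenza positivity 0.10-0.20 (6.1). The share is a statewide figure and the positivity is the study's own expectation. Applying either to routine tests in one tract is an assumption.

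**Step 1, positives per target period** = population × target/100,000 × 0.40 × positivity.

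| Target | All tests | Laboratory tests | Influenza positives |
|---|---|---|---|
| Minimum | 13.3-21.3 | 5.3-8.5 | 0.53-1.70 |
| Suppression | 39.6-63.3 | 15.8-25.3 | 1.58-5.06 |

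**Step 2, positives per 14-day window.** Multiply by 2 if the target is weekly and by 14 if it is daily.

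**Step 3, chance of an apparent halving.** Take two independent Poisson counts with the same mean, so there is no true change. Compute the probability that the first is at least 1 and the second is at most half the first. Halving is an illustrative threshold, because the plan does not state its hot-spot rule at tract level.

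| Target, unit | Mean per 14 days | Apparent halving |
|---|---|---|
| Minimum, weekly | 1.1-3.4 | 34% to 25% |
| Minimum, daily | 7.4-23.8 | 12% to 1% |
| Suppression, weekly | 3.2-10.1 | 26% to 8% |
| Suppression, daily | 22-71 | under 2% |

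In each row the larger percentage goes with the smaller mean.

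**Step 4, does matching help?** The match is on the social vulnerability index, so it does nothing to stabilise counts. If both tracts have the same Poisson mean, the difference between their counts has twice the variance of either one.

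**Step 5, mobile-unit tests.** The plan does not say whether these enter the score. If they do, one deployment adds:
- 25-50 patients (50-100 per week over 2 deployments) × 10-20% = 2.5-10 positives; or
- 200-250 patients (6.1 text) × 10-20% = 20-50 positives.

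Either would be added in visited tracts only.

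**The case against.** The strongest reply is that tract-by-tract reading is not the plan. Items 1 and 1a of 2.1, with 6.5, describe data collected by tract for a matched comparison, and no section calls a single tract improved. That is a fair reading of the intent. But no paired or pooled analysis is written down, so the matched design has no stated way to deliver an answer with a margin of error.

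Second, the size depends on a time unit that the plan does not give. A reader might infer that tract scores are mostly noise whatever the unit. The documents do not support that: on the daily readings an apparent halving occurs in 12% of windows or fewer, and at the daily suppression target in under 2%. Nor is the minimum target the only one; the same sentence gives the suppression target, which is about three times as high (1,582/532 = 2.97).

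Third, the score is not the influenza count. It draws on COVID-19 as well as influenza data, carries a weight for social vulnerability, and has no published formula. The count is a stand-in for its noise, and this limit stands.

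Fourth, a reader might infer that the plan averages tract scores without weights. It does not say so; it is silent on weighting.

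Finally, replacing the score with test positivity would be a debatable change. The mobile unit tests people with symptoms in visited tracts only, which shifts both the number tested and the case mix there. This objection stands, so positivity belongs in a sensitivity analysis.

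**Conclusion.** The concern holds in limited form. The primary comparison is made on census-tract scores over 14 days with no pooling and no measure of chance. Followed literally, it cannot separate an effect from ordinary variation.

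If the testing target is weekly, the problem is material: an unchanged tract appears to halve in 25-34% of windows at the minimum target and in 8-26% at the suppression target. If the target is daily, it is modest at the minimum target (1-12%) and small at the suppression target (under 2%).

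These figures assume Poisson counts, tract-level use of the 40% share and the 10-20% positivity, background laboratory tests only, and a tract that just meets the target. They also assume a tract that was not chosen for a high count. Tracts visited because they were flagged would tend to fall more often by chance, and matching on vulnerability does not address that.

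**What to change.** Amend 2.1 and 6.5 as follows.

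- **Primary result.** One pooled visited-versus-matched comparison of the change in hot-spot score across all deployments. Put matched pair and calendar week in the model, and report an interval clustered by tract.
- **Benchmark.** Judge the result against the distribution of 14-day score changes in the unvisited tracts among the roughly 140 already tracked. This measures chance variation in the score itself, so it does not depend on the missing time unit or on the Poisson assumption.
- **Tract-level output.** Keep each tract's flag and trend descriptive, and state that no tract will be called improved on its own flag.
- **Sensitivity analysis.** Model laboratory influenza positives with tests as the denominator, overdispersion and a tract effect, excluding mobile-unit tests.

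In the same edit, state the time unit of the testing targets and whether mobile-unit tests enter the score.

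The cost is protocol wording and a little more analysis work on data already being collected, with no change to patients or visits. The study gives up tract-level claims.

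### A single statewide laboratory share (about 40%) underlies census-tract scores, so unadjusted comparisons between tracts can partly reflect laboratory share; a contrast against each tract's own baseline is a cheap safeguard

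*Combined protocol and SAP*

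**What the plan says.** Section 3.1 lists the changes made to a county-level hot spot criterion. One concerns scale: "we have narrowed the scope of the population of interest to the census tract". Another sets what the calculations rest upon: "the proportion of the respiratory virus testing performed by TriCore Laboratories relative to the total testing in the State of New Mexico (approximately 40"%). Tract status comes from the laboratory's own records: "Using a longitudinal patient database with an active system to prospectively geocode addresses entered into our system", from which "we are able to determine, at the census tract level, neighborhoods that are at high risk for viral transmission". The social vulnerability index (SVI) is then added: the plan will "incorporate the social vulnerability index as an additional weighted measure to the hot spot or desert score". The weight is not given.

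Testing deserts are described separately in section 3.1, from another source, with "a goal of 532/100,000 or 1582/100,000 COVID-19 or influenza tests for as the minimum target or suppression target, respectively". The 40% is not mentioned there, and no time period is attached to the targets.

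For the primary objective, section 2.1 says: "The hot-spot frequency and hot spot score trend will be measured for each census tract". Item 1a follows the score for 14 days after each visit in the visited tract and in an SVI-matched tract without a visit. Section 6.5 refers only to the score in SVI-paired tracts. It gives no model and no adjustment for the pre-visit level. No section gives a tract, county or metropolitan share, the score formula, or a sensitivity analysis on the share.

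**The concern.** The unit of scoring is the tract, while the correction for tests done elsewhere is a state average. A laboratory's share of testing in a neighbourhood depends on where local clinics send their samples, so it need not equal 40% in each of about 140 tracts. Matching on SVI does not balance it, because SVI does not measure laboratory use.

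Two things are at stake. First, a tract served mainly by other laboratories could look quiet or under-tested, and one served mainly by this laboratory could look like a hot spot, so the mobile unit could be sent to the wrong place. Second, if visited tracts are picked on that reading, their shares may differ systematically from those of tracts picked only for similar SVI. A post-visit comparison of score levels, or of how often tracts cross the hot spot threshold, would then mix laboratory share with transmission.

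**Working it through.** **The plan's figure.** The 40% cannot be reproduced, because section 3.1 gives no test counts behind it.

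**Inputs from the documents.** Statewide share 0.40 and desert targets of 532 and 1,582 tests per 100,000 (3.1); tract population 2,500-4,000 (6.1); matching on SVI with 14 days of follow-up (2.1).

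**Assumptions.** (a) The score uses laboratory counts divided by 0.40 or, equivalently, thresholds multiplied by 0.40. The formula is not stated, but 3.1 describes the source criterion as based on rates. (b) Tract shares s range over 20-60%, for illustration only.

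**1. Reading factor.** Scored rate / true rate = s/0.40.
- s = 0.20: 0.50
- s = 0.30: 0.75
- s = 0.50: 1.25
- s = 0.60: 1.50

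**2. Level contrast.** Apparent ratio = true ratio x (s visited / s matched). With a true ratio of 1:
- 50% against 30%: 0.50/0.30 = 1.67
- 30% against 50%: 0.30/0.50 = 0.60
- 35% against 45%: 0.35/0.45 = 0.78
- 60% against 60%: 1.00, so a shared departure from 40% does no harm here

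**3. Change contrast.** Let both tracts truly fall from 100 to 80, with shares of 50% (visited) and 30% (matched).
- Absolute: visited -20 x 1.25 = -25; matched -20 x 0.75 = -15. The difference is -10, where the truth is 0.
- Relative: visited 100/125 = 0.80; matched 60/75 = 0.80. The ratio is 1.00, as it should be. A stable share cancels.

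**4. Desert threshold, only if the 40% also scales the target.** The cut-off becomes 532 x 0.40 = 212.8 laboratory tests per 100,000. The true rate that just meets it is 212.8/s: 1,064 at s = 0.20 and 355 at s = 0.60. If the target is not scaled, the figures are 532/s instead: 2,660 and 887.

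**5. Size of the counts.** 532 per 100,000 is 13 to 21 tests in a tract of 2,500-4,000, or about 5 to 9 laboratory tests after multiplying by 0.40. In a tract of 3,000 with 10% positivity, one such period gives 3,000 x 0.00532 x 0.40 x 0.10 = 0.64 positives, so a Poisson count is zero in about 53% of periods. If the target is daily, 14 days give about 9 positives.

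**6. The mobile unit's own tests.** Section 6.1 gives 200-250 patients per deployment in its text and 50-100 in its table. Even 50 tests in a tract of 4,000 add 1,250 per 100,000. On an assumed background of 1,582 per 100,000 at a 40% share, the laboratory's share becomes (632.8 + 1,250)/(1,582 + 1,250) = 66%. That is a reading factor of 1.66, in the visited tract only.

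**The case against.** The strongest reply is that much of the mechanism is unseen. The plan says only that calculations are based on the share. It gives no formula, and a score built on positivity or on relative change would be unaffected by a stable share. Section 2.1 does name a score trend, which could be read as a within-tract measure. No tract shares are reported, all tracked tracts lie in one metropolitan area, and a common departure from 40% leaves matched ratios at 1.00. Site choice also depends on SVI and on 20 partner centres, and a poorly ranked site wastes a visit without by itself biasing the comparison.

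Most of this stands, and it limits the point. A reader might infer that tracts are in fact mis-scored, or that a difference in score reflects market share and not transmission. The documents support neither: both the formula and the shares would have to be known. A reader might also take 1,064 and 355 as properties of the plan's desert rule, but the text does not tie the 40% to that rule.

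The reply does not remove the gap. The trend is not defined as relative, hot-spot frequency is a threshold measure, and section 6.5 states no baseline adjustment. As written, the plan allows a comparison that is open to this bias and offers no check on it.

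**Conclusion.** The point holds conditionally. One state-level share underlies tract calculations, and the stated comparison is of post-visit scores between SVI-matched tracts. With a count- or rate-based score and shares that differ between matched tracts, comparisons of level, absolute change and threshold status can partly reflect laboratory share, and site selection can be distorted. The size is s/0.40 for one tract and the ratio of the two shares for a pair: 1.67 for assumed shares of 50% and 30%, and up to 3.0 at the extremes of the assumed range (60% against 20%). Whether any such error exists here, and how large it is, cannot be known from the documents. It is a weakness that is cheap to guard against, not a demonstrated error.

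**What to change.** In sections 3.1 and 6.5:

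- State the score formula, how the 40% enters it, and whether it also applies to the testing-desert targets.
- Make the primary contrast the change in each tract's rate from its own pre-deployment period, visited against matched, on a relative scale. Use a count model (for example Poisson or negative binomial with a log link), because a simple log ratio is undefined in tracts with zero positives.
- Leave the mobile unit's own tests out of the tract rate. Otherwise the share is not stable in visited tracts and no longer cancels.
- Repeat hot-spot classification, site selection and the contrast with tract shares varied over an assumed 20-60%. Vary them separately for visited and matched tracts, since a common shift leaves the ratio unchanged. This step is also needed because a relative contrast does not repair threshold-based hot-spot frequency.
- Use local shares for site selection only where total test counts are available. A county share does not correct a contrast between tracts in the same county, since both receive the same factor.

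The cost is analysis work on data the laboratory already holds, apart from any local totals obtained for site selection; patient procedures do not change. The downside is somewhat more noise in tracts with few positives.
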